## 15.3 Assessments During Treatment

### 15.3.1 Days 1-3 (Mandatory In-clinic)

The assessments or procedures listed below will be performed daily (unless otherwise specified) on Days 1-3 (see Section [15.3.4](#) for assessments/procedures required for discontinuation from the study).

- Study medication administration QID at 8 AM, 1 PM, 6 PM, and 11 PM.

- Effectiveness assessments at estimated time of maximum plasma concentration (Tmax, i.e., 3.5 hours after the first daily dose) including:
  - SOWS-Gossop; and
  - COWS.
- Completion of pre-defined withdrawal treatment goal (e.g., planned detoxification/transition) as assessed by the Principal Investigator (after completion of the SOWS-Gossop and COWS).
- Concomitant medication assessment.
- Vital signs including blood pressure and pulse at rest (sitting [or recumbent if necessary because of an AE]) and standing (if able) before every dose and 3.5 hours after administration of study medication at 8 AM, 1 PM, and 6 PM (7 times per day); respiration and temperature before 8 AM dose only.
- Continuous monitoring for AEs.
- 12-lead ECGs (in duplicate) before the first dose on Day 1 at 8 AM and 3.5 hours ( $\pm 15$  minutes) after dosing.
- A fingerprick blood sample for PK analysis will be collected concurrently with each scheduled ECG.
- Clinical laboratory tests as clinically warranted.
- Complete physical examination 3 to 4 hours after dosing on Day 1 and as clinically warranted.
- C-SSRS (Since Last Visit Version; [Appendix 6](#)) at 3.5 hours after the first dose (8 AM) on Days 1-3.
- A qualitative urine drug screening (by on-site use of “dipsticks”) will be done every day to monitor for contraband.

### 15.3.2 Days 4-7 (In-clinic/Outpatient)

The assessments or procedures listed below will be performed daily (unless otherwise specified) on Days 4-7 (see Section [15.3.4](#) for assessments/procedures required for discontinuation from the study).

- Study medication administration QID at 8 AM, 1 PM, 6 PM, and 11 PM.
- SOWS-Gossop 3.5 hours after the first daily dose during in-clinic treatment; once daily before dosing during outpatient treatment.
- COWS 3.5 hours after the first daily dose during in-clinic treatment; once daily before dosing during outpatient treatment.
- Completion of pre-defined withdrawal treatment goal (e.g., planned detoxification/transition) as assessed by the Principal Investigator (after completion of the SOWS-Gossop and COWS).

- Concomitant medication assessment.
- Pill count and review of subject diary ([Appendix 3](#)) to measure compliance with previous day's doses if being treated as an outpatient.
- Vital signs including blood pressure and pulse at rest (sitting [or recumbent if necessary because of an AE]) and standing (if able) during in-clinic treatment before every dose and 3.5 hours after administration of study medication at 8 AM, 1 PM, and 6 PM (7 times per day); respiration and temperature before 8 AM dose only.
- Vital Signs including blood pressure and pulse at rest (sitting [or recumbent if necessary because of an AE]) and standing (if able) at least once daily before dosing and 3.5 hours after dosing during outpatient treatment. Note that if the subject cannot stay in the clinic for measurement of the 3.5-hour post-dose vital signs required on Days 4-7, they will be given a portable digital blood pressure machine for measurement of their vital signs at this required time point. Subjects will also be provided a diary ([Appendix 3](#)) to record the measurements along with any symptoms of hypotension and/or bradycardia (see list in Section [13.2.2](#)) the subject may have experienced.
- A fingerprick blood sample will be collected during outpatient treatment when the subject reports to the clinic each day (before next scheduled dose) for analysis of plasma lofexidine concentration to monitor compliance.
- AE assessment.
- Clinical laboratory tests as clinically warranted.
- Complete physical examination as clinically warranted.
- C-SSRS (Since Last Visit Version; [Appendix 6](#)) at 3.5 hours after the first dose (8 AM) during in-clinic treatment; once daily before dosing during outpatient treatment.
- Qualitative urine drug screening (by on-site use of "dipsticks") will be done every day in an in-clinic setting to monitor for contraband and every day in an outpatient setting to monitor for illicit drug use.
- Daily clinic visits and completion of subject diary for outpatients.

Subjects not requiring extended lofexidine treatment can be discharged from the study on Day 7 after receipt of at least one dose of study drug and after all end-of-study procedures have been completed (see Section [15.3.4](#)).

### **15.3.3 Days 8-14 (Outpatient Only)**

Study medication is optional on Days 8-14 for subjects continuing to have withdrawal symptoms per the Principal Investigator's judgment. The assessments and procedures listed below will be performed daily (unless otherwise specified) (see Section [15.3.4](#) for assessments/procedures required for discontinuation from the study).

- Daily clinic visits and completion of subject diary.
- SOWS-Gossop before dosing.

- COWS before dosing.
- Completion of pre-defined withdrawal treatment goal (e.g., planned detoxification/transition) as assessed by the Principal Investigator (after completion of the SOWS-Gossop and COWS).
- Concomitant medication assessment.
- Pill count and review of subject diary ([Appendix 3](#)) to measure compliance with previous day's doses.
- Vital Signs, including blood pressure and pulse at rest (sitting [or recumbent if necessary because of an AE]) and standing (if able) at least once daily before dosing and 3.5 hours after dosing on Days 8-13 and once before any dose on Day 14. Note that if subjects cannot stay in the clinic for measurement of the 3.5-hour post-dose vital signs required on Days 8-13, they will be given a portable digital blood pressure machine for measurement of their vital signs at this required time point. Subjects will also be provided a diary ([Appendix 3](#)) to record the measurements along with any symptoms of hypotension and/or bradycardia (see list in Section [13.2.2](#)) the subject may have experienced.
- AE assessment.
- Clinical laboratory tests as clinically warranted.
- Complete physical examination as clinically warranted.
- C-SSRS (Since Last Visit Version; [Appendix 6](#)) before dosing.
- A fingerprick blood sample will be collected during outpatient treatment when the subject reports to the clinic each day (before next scheduled dose) for analysis of plasma lofexidine concentration to monitor compliance.
- Qualitative urine drug screening (by on-site use of "dipsticks") will be done every day in an outpatient setting to monitor for illicit drug use.

#### **15.3.4 Study Discontinuation/End of Study**

Any subject that discontinues from the study, regardless of the reason (see all scenarios listed in Section [14.5.1](#)), will be requested to complete all Study Discontinuation/End of Study assessments and procedures as listed below after the last dose of study medication.

- SOWS-Gossop.
- COWS.
- Completion of pre-defined withdrawal treatment goal (e.g., planned detoxification/transition) as assessed by the Principal Investigator (after completion of the SOWS-Gossop and COWS).
- Concomitant medication assessment.
- Pill count and review of subject diary ([Appendix 3](#)) to measure compliance with previous day's doses if not already performed.

- Vitals signs including blood pressure and pulse at rest (sitting [or recumbent if necessary because of an AE]) and standing (if able); respiration; and temperature.
- AE assessment.
- 12-lead ECGs (in duplicate) before the subject's last dose and after dosing.
- Clinical laboratory tests.
- Complete physical examination (including body weight).
- Pregnancy test.
- Urine drug screen.
- C-SSRS (Since Last Visit version; [Appendix 6](#)).

### 15.3.5 30-Day Telephone Follow-up Contact

A follow-up telephone contact will be attempted 30 days after the subject's last dose and will include an adverse event evaluation and an evaluation of the subject's current treatment status (e.g., relapse, current psychosocial treatment, successful entry into a methadone, buprenorphine or naltrexone program). Repeated attempts will be made to reach the subject (defined as a minimum of 3 telephone calls, followed by sending a letter). If repeated attempts are unsuccessful, this will be recorded in the subject's source document and eCRF.

## 15.4 Effectiveness Assessment Methods

### 15.4.1 Assessment of Completion of Pre-Defined Withdrawal Treatment Goal

The Principal Investigator will indicate if the subject has completed his/her pre-defined withdrawal treatment goal ([Appendix 4](#)) on Days 1-7 by responding to the following question: "Has the subject's withdrawal treatment goal been reached?" Note that, per protocol, subjects are required to continue on their dose of lofexidine through Day 7 even though the subject may have completed his/her withdrawal treatment goal before Day 7. This same assessment will be made at each visit during the 7 days of optional outpatient treatment (Days 8-14). This assessment should be completed after the SOWS-Gossop and COWS assessments.

### 15.4.2 Short Opiate Withdrawal Scale of Gossop (SOWS-Gossop)

The SOWS-Gossop [\[16\]](#) will be completed by the subject at baseline, once daily at 3.5 hours ( $\pm$  10 minutes) after the first dose of study medication during in-clinic treatment and once daily before dosing during outpatient treatment. Note that at the time of each daily evaluation, subjects should consider their symptoms over the last 24-hour period or since the last time the subject took this test. Also, this scale should be completed before completion of the COWS.

The SOWS-Gossop scale assesses subjective symptoms of opioid withdrawal ([Appendix 1](#)). It is a subject-rated scale consisting of 10 items that are scored on a 4-point scale of 0 = none, 1 = mild, 2 = moderate, and 3 = severe (minimum score of 0, maximum score of 30) (see

**Table 2** below). The overall score will be the simple sum of the 10-item scores. Lower observed values in SOWS-Gossop scores indicate a more positive clinical outcome.

Table 2. SOWS-Gossop Scoring Method

Condition	Score			
	None	Mild	Moderate	Severe
Feeling Sick	0	1	2	3
Stomach Cramps	0	1	2	3
Muscle Spasms/Twitching	0	1	2	3
Feeling of Coldness	0	1	2	3
Heart Pounding	0	1	2	3
Muscular Tension	0	1	2	3
Aches and Pains	0	1	2	3
Yawning	0	1	2	3
Runny Eyes	0	1	2	3
Insomnia/Problems Sleeping	0	1	2	3

Note: Possible score range = 0 to 30.

### 15.4.3 Clinical Opiate Withdrawal Scale (COWS)

The COWS [17] will be used to assess the effectiveness of lofexidine in alleviation of opioid withdrawal, and will be completed after the SOWS-Gossop and before the assessment of completion of pre-defined withdrawal treatment goal. It will be completed during screening, at baseline (before dosing on Day 1), once daily at 3.5 hours after the first dose of study medication during in-clinic treatment, and once daily before dosing during outpatient treatment. The COWS is a clinician-administered instrument that rates 11 common opioid withdrawal signs and symptoms (Appendix 2). These include: resting pulse rate; sweating; restlessness; pupil size; bone or joint aches; runny nose or tearing; gastrointestinal (GI) upset; tremor; yawning; anxiety or irritability; and gooseflesh skin. The score for each item reflects the severity of the sign or symptom, and the total scores are grouped as mild (5-12 points), moderate (13-24 points), moderately severe (25-36 points), and severe (>36 points).

## 15.5 Safety Assessment Methods

### 15.5.1 Adverse Events

The occurrence of AEs will be assessed starting at the treatment phase of the protocol (i.e., with the first dose of study drug). Any AE that occurs during screening will be recorded in the subject's Medical History eCRF. The occurrence of Serious Adverse Events (SAEs) will be assessed after signing of the informed consent form.

Adverse events will be assessed and recorded around the same time each day by study staff during in-clinic lofexidine treatment. If an AE requires medical attention, it should be reported to a study physician immediately. A study physician or assigned staff must meet with the subject to assess all medical and psychiatric AEs reported by the subject, as well as those recorded by other study staff. Adverse events will be assessed by asking the subject, "How have you been feeling since I saw you last?" After current AEs are assessed, the study physician or assigned staff must review with the subject and assess any AEs unresolved from the previous day. For each daily AE assessment, details will be recorded in the subject's

source document and AE eCRF, according to the procedures described in Section 16.7, the type of AE and whether it is serious (SAE) or non-serious, severity of each AE, and the relationship to the study agent. These categories are asking for the Principal Investigator or physician designee's best judgment of the severity and relatedness of each AE. The Principal Investigator or physician designee will also record, based on his/her best judgment, whether the AE is secondary to opioid withdrawal (see Section 15.5.1.1). In general, an AE should not be marked as withdrawal related AND related to study medication.

Any study subject with a related AE will be followed until the event is resolved to the satisfaction of the Principal Investigator and Sponsor's Medical Monitor. If the AE is unrelated, the subject will be followed until medically stable, and then will be referred, at the subject's sole expense, for ongoing care and/or treatment, which may include psychological and lifestyle counseling, support groups, or pharmacological and medical treatment.

During outpatient treatment, subjects will be queried about AEs at each daily clinic visit. All subjects will be instructed to contact the study physician or assigned staff if he or she experiences any symptoms of hypotension and/or bradycardia (see list in Section 13.2.2) (especially on standing from a sitting or lying position) and delay additional lofexidine dosing until further instructed.

All reported AEs will be recorded as described above.

#### **15.5.1.1 Withdrawal-Related Adverse Events**

The Principal Investigator or physician designee will also record, based on his/her best judgment, whether the AE is secondary to opioid withdrawal. Individual items reported on the efficacy scales (i.e., SOWS-Gossop, COWS) do not automatically qualify as a withdrawal-related AE unless the subject specifically reports them in response to the non-leading question (i.e., "How have you been feeling since I saw you last?"). In the event a subject reports "withdrawal" or a similar event encompassing a collection of potential withdrawal symptoms, the subject should be asked to elaborate so that each specific symptom can be recorded on the AE eCRF. In general, an AE/SAE should not be marked as withdrawal related AND related to study medication.

#### **15.5.2 Vital Signs**

Vital signs (sitting/standing systolic and diastolic blood pressure, pulse) will be measured at screening for all subjects.

During in-clinic treatment (Days 1-3 mandatory; Days 4-7 if subject receives all lofexidine doses in the clinic), resting (sitting [or recumbent if necessary because of an AE]) and standing (if able) systolic and diastolic blood pressure and pulse will be measured within 30 minutes before every dose and 3.5 hours ( $\pm$ 15 minutes) after administration of study medication at 8 AM, 1 PM, and 6 PM; oral temperature and respiration before 8 AM dose only.

During outpatient treatment (Days 4-14) resting (sitting [or recumbent if necessary because of an AE]) and standing (if able) systolic and diastolic blood pressure and pulse will be

measured at least once daily before dosing and 3.5 hours ( $\pm 30$  minutes) after dosing on Days 4-13 and once before any dose on Day 14. If the subject cannot stay in the clinic for measurement of the 3.5-hour post-dose vital signs required on Days 4-13, they will be given a portable digital blood pressure machine for measurement of their vital signs at this required time point and the values will be recorded in a subject diary ([Appendix 3](#)).

For the orthostatic vital sign (i.e., blood pressure and pulse) readings, subjects will remain at rest for 3 minutes before a vital sign reading, and then stand for 3 minutes before a second vital sign reading is taken. If a subject demonstrates potentially clinically significant vital signs (whether pre- or post-dose), as per the pre-defined criteria detailed in Sections [13.2.2](#) and [13.2.3](#), the event should be recorded on the subject's eCRF as an AE or SAE (see Sections [15.5.1](#), [16.7](#), and [16.8](#)) and the subject should be followed until medically stabilized to the satisfaction of the study physician.

Additionally, when the subject is experiencing blood pressure- or pulse-related symptoms (e.g., lightheaded, dizziness, palpitations), these should be recorded on the subject's eCRF as an AE or SAE (see Sections [15.5.1](#), [16.7](#), and [16.8](#)) even if the vital signs values do not meet the pre-defined criteria detailed in Sections [13.2.2](#) and [13.2.3](#).

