#### **15.5.2 Vital Signs**

Vital signs (sitting/standing systolic and diastolic blood pressure, pulse) will be measured at screening for all subjects.

During in-clinic treatment (Days 1-3 mandatory; Days 4-7 if subject receives all lofexidine doses in the clinic), resting (sitting [or recumbent if necessary because of an AE]) and standing (if able) systolic and diastolic blood pressure and pulse will be measured within 30 minutes before every dose and 3.5 hours ( $\pm 15$  minutes) after administration of study medication at 8 AM, 1 PM, and 6 PM; oral temperature and respiration before 8 AM dose only.

During outpatient treatment (Days 4-14) resting (sitting [or recumbent if necessary because of an AE]) and standing (if able) systolic and diastolic blood pressure and pulse will be measured before an in-clinic dose of lofexidine and 3.5 hours ( $\pm 30$  minutes) after dosing on Days 4-13 and once before any dose on Day 14. If the subject cannot stay in the clinic for measurement of the 3.5-hour post-dose vital signs required on Days 4-13, they will be given a portable digital blood pressure machine for measurement of their vital signs at this required time point and the values will be recorded in a subject diary ([Appendix 3](#)).

For the orthostatic vital sign (i.e., blood pressure and pulse) readings, subjects will remain at rest for 3 minutes before a vital sign reading, and then stand for 3 minutes before a second vital sign reading is taken. If a subject demonstrates potentially clinically significant vital signs (whether pre- or post-dose), as per the pre-defined criteria detailed in Sections [13.2.2](#) and [13.2.3](#), the event should be recorded on the subject's eCRF as an AE or SAE (see Sections [15.5.1](#), [16.7](#), and [16.8](#)) and the subject should be followed until medically stabilized to the satisfaction of the study physician.

Additionally, when the subject is experiencing blood pressure- or pulse-related symptoms (e.g., lightheaded, dizziness, palpitations), these should be recorded on the subject's eCRF as an AE or SAE (see Sections [15.5.1](#), [16.7](#), and [16.8](#)) even if the vital signs values do not meet the pre-defined criteria detailed in Sections [13.2.2](#) and [13.2.3](#).

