#### *Vital Signs Measurements*

Summary statistics for observed and changes from baseline in sitting and standing vital signs, separately, will be tabulated at each follow-up for each vital sign parameter and at post-baseline endpoint for each variable overall and for each co-administration category. All values will be included in the summary of potentially clinically significant vital signs. However, post-baseline repeat/unscheduled assessments will be excluded for the other tabulations.

In addition the number and proportion of subjects having PCS will be tabulated:

- Systolic blood pressure  $\geq 180$  mmHg and an increase of  $\geq 20$  mmHg from baseline
- Systolic blood pressure  $\leq 90$  mmHg and a decrease  $\geq 20$  mmHg from baseline;
- Diastolic blood pressure  $\geq 105$  mmHg and an increase  $\geq 15$  mmHg from baseline;

- Diastolic blood pressure  $\leq 50$  mmHg and a decrease  $\geq 15$  mmHg from baseline; or

Additionally, the number and proportion of subjects having a dose-hold due to a VS measurement will be tabulated as follows:

Resting (sitting [or recumbent if necessary because of an AE])

- Systolic blood pressure  $<90$  mmHg and  $>20\%$  below screen value;
- Diastolic blood pressure  $<50$  mmHg and  $>20\%$  below screen value;
- Pulse  $<50$  bpm and  $>20\%$  below screen value; or
- Symptoms of hypotension and/or bradycardia (e.g., lightheadedness, dizziness).

Orthostatic (after standing for 3 minutes)

- Systolic blood pressure diastolic blood pressure, or pulse  $>25\%$  below recumbent values.

In addition, the number and proportion of subjects meeting the discontinuation Vital Signs criteria will be tabulated as follows:

- Resting systolic blood pressure  $<70$  mmHg;
- Resting diastolic blood pressure  $<40$  mmHg;
- Resting pulse  $<40$  bpm;
- QTcF  $>500$  msec or  $>25\%$  above screen value for both males and females; or
- Syncope.
- Persistent symptomatic hypotension (e.g., hypotension not responding to bed rest or fluids).
- Single occurrence of symptomatic bradycardia (as assessed by Principal Investigator/study physician/assigned staff, regardless of blood pressure) associated with chest pain, shortness of breath, or decreased level of consciousness.

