- Persistent hypertension – resting blood pressure  $\geq 185/110$  mmHg recorded on 3 separate occasions taken at least 5 minutes apart AND within a 1-hour time period. If 2 of 3 readings are  $\geq 185/110$  mmHg (either systolic  $\geq 185$  mmHg or diastolic  $\geq 110$  mmHg) the subject must be discontinued.

All of the above will be summarized overall and for each co-administration category at each study day.

The incidence of missed standing vital signs will be counted for those subjects with a resting blood pressure measurement and a missing standing blood pressure measurement. The count of unique subjects and number of events will be tabulated. Consecutive missing measurements will be counted as one event. Additionally, the number of missed doses and the reason for each missed dose will be presented for each subject and study day.

The number and percentage of subjects with a reduced dose that still met each of the above criterion after the dose reduction will be presented overall and for each co-administration category by study day.

Mean profiles by study day will be presented for sitting and standing blood pressure and pulse rate.

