#### **Section 6.10 Vital Signs Measurements**

Change: Addition of the incidence of missing standing vital signs measurements.

Reason: There is interest in determining the number of subjects who could not stand.

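### The SAP's count of missed standing blood pressures is meant to show who could not stand, but it treats a half-completed home set the same as a true inability to stand

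*Protocol*

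**What the plan says.** The count is defined in SAP Section 6.9, Vital Signs Measurements. Missed standing vital signs are to be "counted for those subjects with a resting blood pressure measurement and a missing standing blood pressure measurement", and both unique subjects and events are tabulated. For events the rule is: "Consecutive missing measurements will be counted as one event". SAP Section 6.10 lists the count as an addition to the protocol's analyses and gives the reason: "There is interest in determining the number of subjects who could not stand".

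Section 6.9 makes one relevant exclusion. Outside the summary of potentially clinically significant values, "post-baseline repeat/unscheduled assessments will be excluded for the other tabulations". A scheduled home reading is neither a repeat nor unscheduled, so it stays in. The same part of the SAP asks for reasons only for missed doses: "the number of missed doses and the reason for each missed dose will be presented for each subject and study day". It asks for none for a missed standing reading.

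Protocol 15.5.2 (current Amendment 02 text) requires outpatients to have resting and, if able, standing values before the in-clinic dose and 3.5 hours after it. For subjects who have to leave before the later set on Days 4-13, the provision is that "they will be given a portable digital blood pressure machine for measurement of their vital signs at this required time point". Their home results go into the diary. The synopsis, 15.3.2 and 15.3.3 say the same. Section 15.5.2 also describes the orthostatic procedure as two steps: three minutes at rest and a reading, then three minutes standing and a second reading.

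**The concern.** When staff take the readings and the protocol asks for a standing value if the subject is able, a resting value with no standing value is reasonable evidence that the subject could not stand. A subject measuring alone at home is different. The resting step can be done and the standing step skipped, or done and not written down. That is exactly the pattern the SAP counts, and nothing in the rule separates the two causes by setting or by reason.

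Safety is the primary objective, and orthostatic hypotension, orthostatic bradycardia and syncope are the protocol's adverse events of special interest. A table added to show how many subjects could not stand should not rise because of gaps in home measurement. The event rule adds a second problem: the number of events does not tell the reader how many readings were missed.

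**Working it through.** The plan gives no figure for this count, so there is nothing to reproduce. The check sets the rule against the measurement schedule and then shows what the rule could do.

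**1. Which sets can be taken at home.** Protocol 15.3.1 gives 7 in-clinic sets a day: 4 before doses and 3 after doses. In the outpatient phase there are 2 sets a day on Days 4-13 (one before the in-clinic dose, one at 3.5 hours) and 1 on Day 14. Only the 3.5-hour set may be taken at home. Leaving the end-of-study set aside, for a subject who becomes an outpatient on Day 4:
- treated to Day 7: 3×7 + 4×2 = 29 sets, up to 4 at home (4/29 = 13.8%);
- treated to Day 14: 3×7 + 10×2 + 1 = 42 sets, up to 10 at home (10/42 = 23.8%).

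**2. How the rule treats a home set.**
- Both values recorded: not counted.
- Neither value recorded: not counted, because the rule needs a resting value.
- Resting value only: counted, whatever the cause.

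**3. Possible effect on the subject count.** Let q be the chance that a home set has a resting value but no standing value for a reason other than inability to stand. The documents give no q; the range below is an assumption. If all k eligible sets are taken at home and omissions are independent, a subject able to stand is counted at least once with probability 1 − (1 − q)^k.

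| q | k = 4 (Days 4-7) | k = 10 (Days 4-13) |
|---|---|---|
| 1% | 1 − 0.99^4 = 3.9% | 1 − 0.99^10 = 9.6% |
| 2% | 1 − 0.98^4 = 7.8% | 1 − 0.98^10 = 18.3% |
| 5% | 1 − 0.95^4 = 18.5% | 1 − 0.95^10 = 40.1% |
| 10% | 1 − 0.90^4 = 34.4% | 1 − 0.90^10 = 65.1% |

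The probability grows with k because one omission is enough for a subject to be counted.

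**4. The event rule.** A subject in clinic who misses the standing reading at every set for two days misses 2×7 = 14 readings, and this is one event. A subject who misses one reading is also one event. The SAP does not say whether consecutive refers to scheduled time points or to days. So it is also unclear whether two home omissions with a complete clinic set between them make one event or two.

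**The case against.** The case against giving this much weight is substantial, and most of it limits the size.

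- The rule is narrower than it may look. A home set skipped altogether is not counted.
- This is one descriptive count. Orthostatic effects are also captured by the special-interest events in SAP Table 2 (orthostatic hypotension, presyncope, syncope), the orthostatic dose-hold tabulation, syncope among the discontinuation criteria, and the standing vital-sign summaries. Protocol 15.5.2 also requires pressure- and pulse-related symptoms to be recorded as adverse events even when no threshold is met.
- Home measurement applies only when the subject cannot stay in clinic, and treatment on Days 8-14 is optional. The probabilities in the table are therefore upper values for a given q, and q may be small.
- Daily visits with diary review, and data queries to sites, should reduce simple recording gaps. The diary form (Appendix 3) is not in the available text, so whether it has a standing field or a reason field cannot be checked.
- Merging consecutive misses does not change the number of subjects, which is the quantity Section 6.10 names.
- Clinic sets can also lack a standing value for non-medical reasons.

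All of these stand. None removes the defect: where a half-completed home set occurs, the rule counts it as the finding of interest, and the SAP uses no field that would separate it.

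A reader might go further and infer that the inpatient-outpatient pattern of this count is uninterpretable. The SAP plans no such comparison; its by-phase summaries are for adverse events and the C-SSRS. A reader might also infer that a well outpatient could score up to 10 events against 1 for an inpatient unable to stand for two days. That needs all 10 home sets to be half completed and one particular meaning of consecutive, so it is an extreme case and not an expected result.

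**Conclusion.** The concern holds as a mismatch between a stated rule and its stated purpose. SAP 6.9 with 6.10 would let incomplete self-measured sets on Days 4-13 enter a count meant to show who could not stand. The error for subjects able to stand runs in one direction, upward. Its size is unknown. The 4%, 18.5% and 34% (4 home sets) and 10%, 40% and 65% (10 home sets), for q of 1%, 5% and 10%, rest on an assumed q, on independent omissions and on every eligible set being taken at home. They are not predictions for the trial, whose overall count also includes subjects who stayed in clinic.

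The documents do not support calling this a gap in participant safety or the trial's main measure of orthostatic harm. No sample size or error rate is affected. A modest change to the SAP would make the table answer the question it was added for.

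**What to change.** In SAP 6.9, tabulate missed standing readings (unique subjects and sets) in two rows: clinic sets measured by staff, and home sets measured by the subject and recorded in the diary. Base the interpretation that a subject could not stand on the clinic row, with the home row shown beside it. Next to the collapsed event count, report the number of sets with a missing standing value over the number of sets with a resting value.

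Keep the home row. Dropping home sets would be debatable: 3.5 hours is the protocol's estimated time of peak concentration, and subjects who measure at home would be left with mainly pre-dose outpatient readings.

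The cost is SAP wording and one or two extra table rows. The split also needs the setting of each reading in the data; the diary is a separate source for home values, but the database fields cannot be checked from the documents. The downside is that inability to stand that occurs only at home appears in the home row and in adverse events, not in the clinic row.
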